**Table 1. Summary of studies investigating association of ACT and outcomes**

Study	Year	Study Design	Patients (n)	Rates of adjunctive therapies	ACT associated with ischemic/thrombotic events?	ACT associated with bleeding?	Comments
Bittl et al 	1998	Post hoc analysis of clinical trial comparing heparin with bivalirudin	4,098	Balloon angioplasty only study, no thienopyridine, no GP IIb/IIIa inhibition	Higher risk of abrupt vessel closure in heparin-treated patients at lower initial ACT  No risk difference observed in bivalirudin treated patients	Bleeding requiring transfusion was not associated with initial ACT result, but was associated with peak ACT for both heparin and bivalirudin groups	ACT was only repeated if procedure>45 minutes or if patient developed intraprocedural ischemic complication (i.e, abrupt vessel closure)  Multivariable adjustment not performed
Chew et al 	2001	Meta analysis of pooled data from 6 trials of GP IIb/IIIa inhibitors	5,216	Majority of patients were angioplasty alone (<8% stenting), no thienopyridine	Reduction in composite ischemic events with increasing ACT, with optimal ACT range of 350 sec-375 sec  In subgroup of GP IIb/IIIa treated patients, there was no association between ACT and composite ischemic events across the ACT range of 275 sec to 375 sec	Peak ACT associated with bleeding, including higher rates of bleeding in patients additionally treated with GP IIb/IIIa inhibitors	Optimal ACT range did not vary when analyzed by procedural duration  Multivariable adjustment not performed
Tolleson et al 	2003	Post hoc analysis of clinical trial comparing heparin with eptifibatide	2,064	High rates of dual antiplatelet therapy (97%) and coronary stenting (97%)	No association between ACT at time of device activation and ischemic events (p=0.43). No increased risk of ischemic complications at low ACT values (as low as 200 sec).	No association between ACT and major bleeding (p=0.9). Higher ACT values associated with bleeding among GP IIb/IIIa treated patients	The lowest rate of ischemic events were seen in the lowest ACT tertile, with similar observation among GP IIb/IIIa treated patients  Lower-doses of weight-adjusted heparin used  Lower profile vascular devices
Brenner et al 	2004	Meta-analysis of pooled data from 4 trials	9,974	Clopidogrel (81%), GP IIb/IIIa inhibitors (89%), and coronary stents (93%)	No association between peak ACT and composite ischemic events (p=0.40)	Higher peak ACTs were associated with bleeding (p=0.01)	No interaction between ACT and ischemic or bleeding outcomes in cohorts of patients presenting with unstable angina or diabetes  ACT data missing in 16% of patients
Rajpurohit et al 	2016	Mayo Clinic PCI Registry/DataMart	12,055	High rates of clopidogrel (98%) and coronary stenting (93%)	No association between ACT at time of device activation and ischemic or thrombotic events	No association between ACT at time of device activation and clinically overt bleeding	Largest study on topic to date  Increasing ACT associated with MI risk in women at 1 year

#### F. Statistical Considerations:

**F1. Randomization and blinding:** Patients will be randomized (1:1:1) to one of the three ACT target groups (low, medium, or high) using a dynamic minimization algorithm so as to optimize the likelihood that balance between the low, medium, and high ACT target groups will be

achieved with respect to sex (male or female) and glomerular filtration rate (30 to 59 ml/min/1.73m^2 or ≥60 ml/min/1.73m^2). The algorithm will be implemented in RAVE RTSM, a secure web-based interface, and accessed by the study coordinator or other appointed study personnel. Randomization will be conducted after the diagnostic portion of the procedure on only patients who will require ACT monitoring. Since eligible patients will require ACT monitoring during PCI, we will not conduct the study in a strictly blinded fashion. However, study participants will not be informed of their randomization assignment.

**F2. Data collection and handling:** Electronic case report forms along with a corresponding secure REDCap database will be created for data collection (29). Data to be collected will include baseline demographics, comorbidities, procedural variables, in-hospital events, NACE component, and adverse events.

**F3: Definition of study outcomes:** Study endpoints are summarized in Appendix II.

**F3.1 Primary study endpoint:** Our **primary study endpoint is bleeding** and is defined as either a Bleeding Academic Research Consortium (BARC) hemorrhage grade of 1, 2, 3, or 5 or an EASY hematoma scale grade of I-V from the time of PCI to the time the patient is discharged from the hospital.

**F3.2 Primary safety endpoint:** Our **primary safety endpoint is a composite of net adverse clinical events (NACE) and stent thrombosis**, as defined by the Academic Research Consortium, from the time of PCI to the time the patient is discharged from the hospital.

**F3.2.1 NACE** is the composite of all-cause mortality, myocardial infarction (MI), stroke, target lesion revascularization, and major bleeding within 30 days after PCI.

**F3.2.2 MI** will be defined as any two of the following 3 criteria: 1) chest pain for at least 20 minutes; 2) elevation of cardiac biomarkers, preferably troponin, above the laboratory upper limit of normal; and 3) new pathological Q wave on electrocardiogram.

**F3.3.3 Stroke** will have occurred if post-PCI neurological symptom is confirmed as a stroke by a consultant neurologist at Mayo Clinic with documentation on appropriate neuroimaging (CT or MRI).

**F3.3.4 Major bleeding** will be defined as BARC grade 3 or 5 or EASY grade ≥III.

**F3.3.5 Target vessel revascularization** will be defined as clinically driven revascularization, either by percutaneous or surgical means.

**F3.3.6 Intra-procedural events** would include both bleeding and thrombotic complications. Intra-procedural thrombus will be defined as a visible filling defect noted by the primary operator on the guiding catheter or intracoronary wire or device on selective angiogram.

**F3.4** The study definition of non-inferiority will be defined based on the 95% confidence interval for the difference in proportions of patients with NACE in the low and high ACT target groups,  $\Delta = p^L - p^H$ , with a lower limit of  $\Delta_L$  and an upper limit of  $\Delta_U$ . Low ACT target will be considered to be non-inferior to high ACT target if one of the following holds, depending on the estimate  $p^H$  :

- $\Delta_U < 0.12$  if  $p^H \geq 0.12$
- $\Delta_U < p^H$  if  $0.04 < p^H < 0.12$
- $\Delta_U < 0.04$  if  $p^H \leq 0.04$

Note that italicized version are the theoretical proportions and the estimates are not italicized.

**F.4. Sample size determination:** Recognizing the limitations of previously performed studies regarding ACT and risk of bleeding, including variability in definitions of bleeding, we estimate that the highest ACT target group will experience the in-hospital primary outcome at a rate of 25%, while the lowest ACT target will experience the in-hospital primary outcome at a rate of 5%. A **sample size of 504 patients** was determined to ensure more than 80% power at the

two-sided overall 5% significance level with Bonferroni adjustment for multiple testing ( $p$  value  $\leq 0.025$  considered as statistically significant) to detect an absolute difference in in-hospital bleeding (Aim 1) between the low ACT target and the medium ACT target (ie. 5% vs. 15%) in addition to a 20% absolute difference between the low ACT target and the high ACT target (ie. 5% vs. 25%). The power was estimated on the basis of 5000 simulations. Patients meeting eligibility criteria for the study and who consent for participation but that do not undergo randomization due to either not receiving intracoronary diagnostic imaging (IVUS/OCT) or physiologic testing (iFR/FFR) or PCI will be entered into the ACT registry and observed for clinical events, including 30-day outcomes. The reason these patients are not categorized as screen failures is because the final criterion for eligibility is receipt of PCI, a criterion that is not known until the coronary angiogram is performed which is after patients have signed informed consent. Because patients receive moderate sedation during their procedure as part of standard of care, ethical and scientific prudence dictates that informed consent be obtained prior to procedural start. True screen failures, therefore, are those subjects not meeting study inclusion or exclusion criteria. . Based on current lab practice patterns at our institution, it is anticipated that approximately 20% of patients who enroll in the study will not require ACT monitoring after the diagnostic portion of the procedure, therefore we intend to consent up to 780 patients. In 2016, there were 240 PCI procedures and 220 adjunctive coronary imaging/physiology procedures (Fractional Flow Reserve = 158, Intravascular Ultrasound = 59, Optical Coherence Tomography = 12) establishing the feasibility of performing the study and meeting patient accrual targets over an **18 - 24 month period.**

We also considered the implications of this samples size with the other primary aims. For purposes of estimating the incidence of our study endpoint and safety endpoint (Aim 2), a sample size of 504 with equal allocation to each of the three study arms would produce a two-sided 95% confidence interval with a width of 0.15 or less using the Wilson score method. This sample size would also ensure more than 80% power to show evidence of non-inferiority for our primary safety endpoint (NACE, Aim 3) in patients with a low ACT target compared to those with a high ACT target according to the above criteria (section F3.4) when the low and high ACT targets are the same with respect to NACE assuming the probability of NACE with a high ACT target is 12% or more. A review of the published literature had a median estimated rate of 12% for NACE (range 4% to 20% (Table 2).

Table 2.

Study	Hematoma Rate (%)	Major bleeding Rate (%)	NACE Rate (%)	Mean ACT range (sec)	Comments
Petroglou et al (25)	18	3	NR	147	Mostly diagnostic procedures, all radial cases, 5F sheaths, no high risk patients
Jolly SS (26)	3	3	4	NR	Acute coronary syndrome patients, strict bleeding definitions
Bertrand OF (27)	5	1	20	315	All radial cases

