The pQint-of-care PracTice to IMProve use of AnticoaguLation (OPTIMAL)-ACT trial is a prospective, randomized, investigator-initiated, trial to determine the optimal ACT target value in patients undergoing PCI. This will be the first prospective outcomes trial powered to identify the optimal ACT target range for reducing the rate of in-hospital bleeding (Bleeding Academic Research Consortium and EASY grading defined (Appendix I)). Different bleeding definitions will be used to account for shift in access site practice from femoral to radial, both here at Mayo Clinic Florida, and in the United States. In addition, the EASY grading scale is unique to transradial catheterization and complications related to bleeding may be more frequent among women (13). Rates of net adverse cardiovascular events (NACE) (defined as all-cause mortality, myocardial infarction (MI), stroke, or bleeding) would be identified as a primary safety endpoint in the trial. We aim to test the hypothesis that lower ACT target values, as compared to higher ACT target values, are associated with lower risk of bleeding without compromising efficacy as assessed by the primary safety endpoint. This finding would have significant implications for improving the safety of PCI by reducing bleeding complications.

**A. Significance:** The significance of the study proposal can be highlighted by 1) the recognition of the burden of coronary artery disease (CAD), 2) the widespread adoption and performance of PCI, and 3) the limited data regarding appropriate anticoagulation intensity during PCI. CAD causes 1 out of 6 deaths in the United States. Annually, over 600,000 patients suffer a coronary event, defined as a first hospitalized myocardial infarction or CAD-related death (14). Improvements in adherence to guideline-recommended therapies for patients with ischemic heart disease, including use of coronary revascularization procedures, have impacted the decline in deaths related to cardiovascular disease over the past several years. PCI is performed commonly in the United States with an estimated 490,000 procedures in 2010 alone (15). In patients with acute coronary syndromes, early revascularization with PCI has been

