B.1.4 Aim 4 (Secondary): We aim to study the impact of sex, access-site (i.e., radial vs femoral), and concomitant use of glycoprotein (GP) IIb/IIIa inhibitors on the association of ACT target with bleeding. It has been shown that female sex is associated with higher ACT targets during PCI (17), and work from our group has shown an important observed interaction with myocardial infarction risk in women, but not men, with ACT targets >350 seconds(18). This observation of a potential differential sex-specific interaction has not previously been reported and requires validation in a prospective study. In addition, it has previously been shown that women appear to be at higher risk for developing forearm bleeding complications after transradial catheterization. The use of transradial PCI has steadily increased in the United States, though adoption of this technique remains lower than that observed in Canada and Europe. However, recent internal PCI data from the cardiac catheterization laboratory at Mayo Clinic Rochester has shown increasing utilization of the radial artery for PCI, now over 50%. At Mayo Clinic Florida, the percentage of radial access is over 70% and is considered the default access site for catheterization. It remains unknown whether ACT targets can be similarly interpreted for radial PCI, as these original targets were derived from studies in primarily transfemoral access cohorts with larger vascular access sheaths. Finally, the additional use of GP IIb/IIIa inhibitors in UFH-treated patients has been associated with higher rates of major and minor bleeding (9), thus lower ACT target values (i.e., 200-250 sec) are recommended in patients concomitantly treated with these agents. In the Mayo Clinic experience, there was no apparent interaction by GP IIb/IIIa inhibitor status when testing the association of ACT values to outcomes, however, baseline characteristics of groups receiving or not receiving these agents differed and residual confounding may have been present (18). The OPTIMAL-ACT trial will incorporate a pre-specified analysis with specific ACT targets in patients receiving GP IIb/IIIa inhibitors to better understand ACT targets and outcomes.

B.1.5 Aim 5 (Exploratory): We will explore the association of ACT targets with individual components of NACE and stent thrombosis for purposes of hypothesis generation.

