## Appendix I

### Bleeding Academic Research Consortium (BARC) Standard Bleeding Definition(26)

BARC 0	No bleeding
BARC 1	Non-actionable bleeding
BARC 2	Actionable bleeding, even if on imaging alone, that meets one of the following:1) requires non-surgical (medical) intervention by healthcare personnel; 2) leads to hospitalization or escalation in level of care; 3) prompts evaluation.
BARC 3a	Overt bleeding AND hemoglobin drop 3 to 5 g/dL OR blood transfusion
BARC 3b	Overt bleeding AND hemoglobin drop $\geq 5$ OR cardiac tamponade, bleeding requiring surgical intervention for control, need for intravenous vasopressor
BARC 3c	Intracranial/intraspinal hemorrhage or intraocular hemorrhage with any visual impairment
BARC 4	CABG-related bleeding
BARC 5	Probable or definite fatal bleeding

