### EASY Hematoma Classification Scale

## Appendix II

### Optimal Target of Activated Clotting Time During Percutaneous Coronary Intervention and Outcomes: The OPTIMAL-ACT Trial

#### Study Endpoint Definitions:

##### Bleeding

-EASY hematoma classification after Transradial/Ulnar PCI

Type 1: less than 5cm in diameter from puncture site

Type 2: 5-10 cm in diameter from puncture site

Type 3: >10 cm in diameter but below the elbow limited to the forearm

Type 4:>10 cm in diameter and extends above the elbow

Type 5: any bleeding location with compartment syndrome (ischemic threat to the limb)

-BARC 2, 3, or 5 bleeding using BARC defined bleeding scale

BARC 0	No bleeding
BARC 1	Non-actionable bleeding
BARC 2	Actionable bleeding, even if on imaging alone, that meets one of the following:1) requires non-surgical (medical) intervention by healthcare personnel; 2) leads to hospitalization or escalation in level of care; 3) prompts evaluation.
BARC 3a	Overt bleeding AND hemoglobin drop 3 to 5 g/dL OR blood transfusion
BARC 3b	Overt bleeding AND hemoglobin drop $\geq 5$ OR cardiac tamponade, bleeding requiring surgical intervention for control, need for intravenous vasopressor
BARC 3c	Intracranial/intraspinal hemorrhage or intraocular hemorrhage with any visual impairment
BARC 4	CABG-related bleeding
BARC 5	Probable or definite fatal bleeding

Net Adverse Clinical Events (composite of all-cause mortality, myocardial infarction, stroke, target lesion revascularization, or bleeding)

Stent thrombosis (ST) :

Definite (ST): ACS with angiography or autopsy evidence of stent thrombosis.

Probable (ST): Unexplained death within 30 days of index procedure or acute myocardial infarction involving the target-vessel territory without angiographic confirmation.

Myocardial infarction: presence of 2 of the following: ischemic symptoms; elevation of cardiac troponin  $>99^{\text{th}}$  percentile of lab upper reference range with typical rise and fall; ECG changes compatible with infarction. For cardiac troponin elevated prior to PCI due to myocardial infarction, the subsequent troponin would need to be increased by 20% or more than the previous value to be considered an endpoint event.

Stroke: Focal loss of neurological function caused by an ischemic or hemorrhagic insult, with residual symptoms lasting at least 24 hours, and confirmed on neuroimaging (CT or MRI) with final impression deemed as stroke by a consulting neurologist

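### Major bleeding has a lower threshold after radial than after femoral access (EASY III alone suffices), which changes what NACE and its non-inferiority margin measure

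*Combined protocol and SAP*

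**What the plan says.** **The scales.** The introductory Rationale states that "the EASY grading scale is unique to transradial catheterization", and Appendix II heads the scale "EASY hematoma classification after Transradial/Ulnar PCI". No size-based scale is given for femoral access. The third EASY grade reads "Type 3: >10 cm in diameter but below the elbow limited to the forearm". Type 4 extends above the elbow, and type 5 is any location with compartment syndrome, so the scale is tied to radial or ulnar access rather than strictly to the forearm. In Appendix I the lowest BARC 3 grade, 3a, is "Overt bleeding AND hemoglobin drop 3 to 5 g/dL OR blood transfusion".

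**Major bleeding and NACE.** F3.3.4 says major bleeding "will be defined as BARC grade 3 or 5 or EASY grade ≥III". F3.2.1 makes major bleeding a component of 30-day NACE. The introductory Rationale and the NACE line of Appendix II say only bleeding, without restricting it to major. F3.4 takes the non-inferiority margin from the observed high-arm NACE rate: 4 points at or below 4%, 12 points at or above 12%, and the rate itself in between.

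**In-hospital bleeding and Aim 4.** F3.1 defines the primary endpoint by a BARC "hemorrhage grade of 1, 2, 3, or 5 or an EASY hematoma scale grade of I-V", and section D agrees. Appendix II instead lists "BARC 2, 3, or 5 bleeding using BARC defined bleeding scale" alongside EASY types 1 to 5, leaving out BARC 1. B.1.4 (Aim 4) asks how access site affects the link between ACT target and bleeding. F5.3 answers with a Cochran-Mantel-Haenszel (CMH) test on in-hospital bleeding and stratified relative risks.

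**Access site.** B.1.4 puts radial access above 70% at this site. F1 randomizes after the diagnostic portion and minimizes on sex and GFR only.

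**The concern.** A hematoma over 10 cm with no BARC 3 feature is major bleeding, and hence a NACE event, after radial access. A hematoma of the same size after femoral access is at most BARC 1 or 2 and is not. Most of the trial therefore has a more easily met bleeding component than the rest.

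Two things are at stake in Aim 3. First, NACE partly counts large but otherwise uncomplicated forearm hematomas on the same footing as death, infarction and stroke. Second, because F3.4 reads the margin off the observed high-arm rate, such events in the high arm widen the margin. If a low target reduces them, they also cancel part of any ischemic excess in the low arm. The trial's hypothesis is less bleeding with similar ischemic event rates, so a non-inferiority finding carried by these hematomas would be easy to over-read.

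For Aim 4, a radial-femoral contrast in relative risk could reflect how hematomas are recorded at each site as well as how ACT acts there.

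**Working it through.** **1. The plan's own figure.** Inputs: 168 per arm (504 in three equal arms, section F.4), the 95% Newcombe score interval (F5.2), and the F3.4 margins. The probability of declaring non-inferiority is the sum, over all pairs of event counts, of binomial(168, pL) × binomial(168, pH) wherever the upper Newcombe limit of the difference is below the margin set by the observed high-arm rate. With equal true rates this gives 81.0% at 12% and 84.5% at 15%, in line with the stated power above 80%. At 20% it is 78.8%, just under, which does not affect this point.

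**2. Share of NACE from the EASY-only rule.** Assume 70% radial, all other NACE 8%, and EASY III-or-higher without any other NACE event in 1% to 4% of radial patients. Radial NACE is 9% to 12% and femoral NACE is 8%.
- At 1%: pooled NACE = 8 + 0.7 × 1 = 8.7%; EASY-only share = 0.7/8.7 = 8%.
- At 4%: pooled NACE = 8 + 0.7 × 4 = 10.8%; EASY-only share = 2.8/10.8 = 26%.

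**3. Effect on the Aim 3 decision.** Assume other NACE is 9% in the low arm and 6% in the high arm, a 3-point excess. Then pL = 9 + 0.7 × eL and pH = 6 + 0.7 × eH, where e is the EASY-only percentage among radial patients. All three values of pH lie between 4% and 12%, so at the true rate the margin equals pH.

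| eL vs eH | pL | pH (= margin) | True difference | Chance of declaring non-inferiority |
|---|---|---|---|---|
| none | 9.0% | 6.0% | 3.0 points | 24% |
| 1% vs 2% | 9.7% | 7.4% | 2.3 points | 39% |
| 2% vs 4% | 10.4% | 8.8% | 1.6 points | 55% |

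The margin grows while the difference shrinks, although the non-EASY excess is 3 points in every row.

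**4. Aim 4.** The F5.3 outcome is in-hospital bleeding, so the major-bleeding rule does not enter it.
- Under F3.1, a femoral hematoma can count as BARC 1 or 2. What remains is ascertainment: radial hematomas have a size scale, and femoral ones depend on someone recording a BARC grade.
- Under Appendix II, a radial hematoma under 5 cm counts as EASY type 1, but the same non-actionable femoral hematoma is BARC 1 and does not. Here the asymmetry is in the definition.
- Take the planning rates of 5% low and 25% high. If half of femoral events go uncounted, regardless of arm, the femoral rates are 2.5% and 12.5%: the risk difference falls from 20 to 10 points, but the relative risk stays 0.20.
- If EASY adds hematomas unrelated to ACT in 5% of radial patients, independently of other bleeding, the radial relative risk becomes (1 − 0.95 × 0.95)/(1 − 0.75 × 0.95) = 0.0975/0.2875 = 0.34. At 10% it is (1 − 0.95 × 0.90)/(1 − 0.75 × 0.90) = 0.145/0.325 = 0.45.

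**5. Chance imbalance.** With 70% radial and no balancing on access, the difference in radial share between two arms has SD √(2 × 0.7 × 0.3/168) = 0.05, so a 95% range of about ±10 points.

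**The case against.** **The two scales are deliberate.** The introductory Rationale says that more than one bleeding definition is used because practice has moved from femoral to radial. That justifies collecting EASY. It does not explain why EASY III is equated with BARC 3 or 5, and it gives no rule for making the sites comparable.

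**NACE is a net endpoint, so offsetting is intended.** This stands in principle. What is open is whether a size-only hematoma, countable at one access site, should carry the same weight in the offset as a BARC 3 bleed.

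**The wording of NACE is unsettled.** If the unrestricted wording in the introductory Rationale and Appendix II governs, the EASY III threshold drops out of NACE. This stands: the point depends on F3.2.1. It is also a reason to settle the text.

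**The rates are assumed.** This stands too. Table 2 gives total hematoma rates of 18%, 3% and 5%, so hematomas over 10 cm in 4% of radial patients is already a high value against two of the three studies.

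**A reader might infer that Aim 4 fails.** For example, if hematomas over 10 cm fall from 8% to 4% at both sites with BARC 3 or 5 fixed at 2%, major bleeding shows a relative risk of 6/10 = 0.60 in radial and 2/2 = 1.00 in femoral patients. The documents do not support carrying this into Aim 4, because no analysis of major bleeding by access site is planned. On the F3.1 endpoint, femoral hematomas of that size count as BARC 1 or 2, and both sites give 6% versus 10%. Within each access stratum all arms share one instrument.

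**Removing EASY from major bleeding outright has a price.** With equal arms, the calculation of step 1 gives 81% power at 12% NACE, 74% at 10% and 66% at 8%. This is why the remedy is a supportive analysis and not a new endpoint.

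**Conclusion.** The point holds for NACE as F3.2.1 defines it. Radial patients have a lower major-bleeding threshold than femoral patients, and EASY-only events can materially affect the Aim 3 conclusion through both the margin and the difference. On the assumed 3-point excess, the chance of declaring non-inferiority rises from 24% to 39% or 55%. These figures rest on 70% radial access, additive EASY-only events, and rates that the documents do not supply. The direction follows from F3.4 when the high-arm rate lies between 4% and 12% and a low target reduces these events.

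A reader might also infer that the low-versus-high comparison is biased. It is not: access is already established when patients are randomized, and the same scale applies to every arm within a site. Chance imbalance in radial share adds noise, not systematic error.

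For Aim 4 the problem is smaller: definitional if Appendix II governs, otherwise one of ascertainment. Separately, the CMH test conditions on access site and does not test whether the ACT effect differs between sites, so any claim of a difference would rest on comparing stratum relative risks by eye.

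**What to change.** Keep the stated endpoints and make these changes:

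1. **F5.2, Aim 3:** pre-specify a supportive NACE non-inferiority analysis in which major bleeding is BARC 3 or 5 for every patient, and report EASY III-V separately by arm.
2. **F5.3:** report relative risks by access site on BARC-graded bleeding, one scale for both sites, with an ACT-by-access interaction test and EASY as a radial-only description. State how femoral hematomas are measured and graded.
3. **Reconcile the definitions:** F3.1 and Appendix II on whether BARC 1 counts; and F3.2.1 with the introductory Rationale and Appendix II on whether NACE takes major bleeding or any bleeding.
4. **F1:** add access site as a third minimization factor. It is known at randomization and already used in the F5.3 analyses.

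The cost is wording, a few extra analyses and one more factor in the randomization system. The supportive NACE analysis will have fewer events and less power, so it should be labelled supportive. The interaction test will also be weak, with about 0.3 × 168 = 50 femoral patients per arm if 30% are femoral, and should be read as an estimate with its interval.
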